5.4.5 Inventory of Study Interventions

All study drugs shipped to the study site should be accompanied by a quality control report, shipping list, and a receipt confirmation form for site personnel to use. The shipping of study drugs must have complete written documentation, which typically includes the name or code of the study drug, dosage form, specification, lot number or drug code, quantity, expiration date, sponsor, manufacturing entity, packaging type, storage requirements, recipient institution and address, contact information, shipping date, transportation method, and temperature monitoring measures during transit.

Returned study drugs should not be reused in the study. Only after confirming the balance of the quantities of distributed, used, and returned study vaccines can unused

and returned study vaccines be destroyed. Destruction must be fully documented, including at least the reason for destruction, date of destruction, relevant lot numbers and/or drug codes, actual quantity destroyed, person responsible for destruction, and supervisor. Destruction records are retained by the sponsor.

5.4.6 Reserve vaccine

Sixty reserve vaccine doses will be prepared, with 30 doses each of the experimental vaccine and the active control vaccine. If a study vaccine is found to be damaged during the study, the investigator can obtain the reserve vaccine number for the corresponding group through the randomization system and administer the reserve vaccine labeled with the appropriate vaccine number. (The investigator only sees the randomization number; the true group assignments for the study and reserve vaccines are pre-loaded into the system and remain blinded throughout the study. Additional reserve doses may be added if the existing stock is insufficient.)

5.5 Subject Assignment, Randomization, and Blinding

5.5.1 Randomization of Subjects

Subject randomization occurs after screening. Eligible subjects are assigned a study number in sequential order, which is used to identify all procedures after enrollment. A total of 300 subjects aged 50 and above will be randomly assigned to the experimental or control group in a 1:1 ratio. The central randomization system matches each subject assigned group with a corresponding vaccine number, and subjects receive the vaccine according to this number. For further details, see Section 3.1.

5.5.2 Randomization

This study uses block randomization to allocate subjects to the experimental and control groups in a 1:1 ratio. The central randomization system assigns each subject group with a corresponding vaccine number. Researchers strictly follow the assigned vaccine number to obtain and administer the study vaccine.

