Age	Aged 50 and older				
Sex	Male and female (relatively balanced)				
Inclusion criteria	
 1. Age 50 years or older on the day of enrollment, regardless of gender, and able to provide legal identification. 2. Able to understand the trial procedures, voluntarily agree to participate in the study, and sign the "Informed Consent Form." 3. Female subjects are not pregnant or lactating. Female subjects with childbearing potential should take reliable contraceptive measures, and have no pregnancy and fertility plan within 8 months; 4. Axillary temperature \leq 37.0°C/99.0°F on the day of enrollment. 5. Able to attend all scheduled follow-up visits and able to comply with protocol requirements. 				

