The seroprevalence of VZV-IgG exceeds 90% in most adult populations, therefore, substantial individuals are at risk of developing HZ. Age is considered as the most common risk factor for shingles, and the incidence is relatively stable until the age of 40 years, with 2-3 in 1000 per year, and then gradually increases with age, with 5 in 1000 per year at the age of 50-59, and 10 in 1000 per year at ≥ 60 years [CDC, 2008; Oxman, 2005]. Although most data on the incidence of shingles comes from the United States (the Americas) and Europe, the available data indicate that the incidence of shingles is similar in other parts of the world (including Japan, South Korea, Australia and Latin America, mainland China).

About more than half of HZ cases occur in adults over 60, and >85 elders have a 50% chance of having shingles in their lives [Oxman, 2005]. Older patients also have the

highest risk of developing PHN, with those aged 70 years and older representing 18–50% of PHN [Oxman, 2005; Scott, 2006]. Patients with impaired cell-mediated immunity (CMI) due to disease, medication, medical intervention, or advanced age are at increased risk for HZ [Cohen, 2007].

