3.2.3 Phase I/II Clinical Trial Data

The recombinant zoster vaccine developed by our company has completed Phase I and Phase II clinical trial, evaluating its safety, tolerability, and immunogenicity in healthy individuals aged 50 to 70.

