4.2 The selection basis for the study population

Since the LZ901-330 control vaccine is a Recombinant Zoster Vaccine (RZV, ShingrixTM) developed by GlaxoSmithKline Biologicals SA, which is approved for use in adults aged 50 years and older, the recruitment age for both the experimental and control groups in the LZ901-330 study is set to 50 years and older.

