8.2 Sample Size Determination

Assuming that, 30 days after full immunization, the proportion of gE-specific CD4+ T cell activation with two or more cytokines (IFN- γ , TNF- α , IL-2, CD40L) is 85% in the experimental vaccine group and 75% in the active control group, and the proportion of gE-specific CD8+ T cell activation with two or more cytokines is 55% in the experimental vaccine group and 45% in the active control group, with an assumed dropout rate of 10%, a sample size of 150 subjects per group will yield 135 evaluable subjects per group. At a one-sided significance level of 0.025, this sample size provides approximately 90% power to test the above non-inferiority hypothesis.

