8.4.2 Cellular Immunogenicity

For both the experimental vaccine group and the active control vaccine group, the proportion of gE-specific CD4+ T cell and CD8+ T cell activation with at least two cytokines (IFN- γ , TNF- α , IL-2, CD40L) at 30 days post-full immunization will be calculated along with their 95% confidence intervals (using the Clopper-Pearson method). The difference in proportions between the experimental vaccine group and the active control group and its 95% confidence interval (using the Miettinen and Nurminen method) will also be calculated. If the lower limit of the 95% confidence interval for the difference is greater than -10%, non-inferiority is established. Cellular immunogenicity analysis will primarily be based on the per-protocol set.

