8.4.3 Humoral Immunogenicity

Thirty days after full immunization, the anti-gE antibody concentration will undergo a logarithmic transformation, and an analysis of covariance model will be used to analyze the data. In this model, the logarithmic transformation of the antibody concentration at 30 days post-full immunization will be the dependent variable, the logarithmic transformation of the pre-immunization antibody concentration will be the covariate, and the group will be the fixed effect. Based on this model, the least squares mean of the log-transformed geometric mean concentration (GMC) of anti-gE antibodies at 30 days post-full immunization for each group and the between-group difference (experimental vaccine group - active control vaccine group) will be calculated. After

back-transformation, the GMC of anti-gE antibodies at 30 days post-full immunization for each group and their 95% confidence intervals, as well as the between-group ratio (experimental vaccine group / active control vaccine group) and its 95% confidence interval, will be computed.

The seroconversion rate of anti-gE antibodies at 30 days post-full immunization (defined as at least a fourfold increase in antibody levels post-immunization) will be calculated for both the experimental vaccine group and the active control vaccine group. The 95% confidence interval for each group rate will be calculated using the Clopper-Pearson method.

The geometric mean fold rise in anti-gE antibodies from pre-immunization (Day 0) to 30 days post-full immunization will be calculated for each group, along with its 95% confidence interval.

Reverse cumulative distribution plots of anti-gE antibody titers will be created separately for the experimental vaccine group and the active control vaccine group at pre-immunization and at 30 days post-full immunization.

Humoral immunogenicity analysis will primarily be based on the per-protocol set.

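### Enrolment runs past the 50-70 age range of the reported LZ901 data, but allocation, the primary interval and the ANCOVA take no account of age: no bias, but a little balance and precision are given up

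*Protocol*

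**What the plan says.** Section 4.2 takes the age range from the comparator's approval: "the recruitment age for both the experimental and control groups in the LZ901-330 study is set to 50 years and older". The inclusion criteria (4.3) set no upper age limit, and the protocol gives no minimum number of older subjects.

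Section 3.2.3 describes the completed Phase I and II trials of LZ901 as "evaluating its safety, tolerability, and immunogenicity in healthy individuals aged 50 to 70". Section 1.1 names as a risk factor for zoster "impaired cell-mediated immunity (CMI) due to disease, medication, medical intervention, or advanced age". The primary endpoint is a cell-mediated response.

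On allocation, 5.5.2 says: "This study uses block randomization to allocate subjects to the experimental and control groups in a 1:1 ratio". Sections 5.1.4 and 5.5.1 describe the same central 1:1 scheme, also without a stratification factor.

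For the primary comparison, 8.4.2 specifies one difference per cell type, and "its 95% confidence interval (using the Miettinen and Nurminen method) will also be calculated". Its lower limit is set against -10%, with no stratification. For antibodies, 8.4.3 specifies an ANCOVA in which log baseline concentration "will be the covariate, and the group will be the fixed effect". Age is not a term.

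**The concern.** By the protocol's own account, age bears on the type of response that the primary endpoint measures, and the trial admits an age range for which it reports no LZ901 Phase I/II results. Age is known before allocation, since date of birth is recorded at screening (5.1.3). A baseline factor that plausibly predicts the endpoint is normally worth balancing and adjusting for.

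Two modest things are at stake. A chance difference between arms in the share over 70 shifts the observed difference, which is judged against a fixed 10-point margin. And an unstratified interval counts the age-related spread in response as noise, which costs some power on CD8+, the endpoint with less to spare.

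The allocation part cannot be left for later, because a stratum has to be in place before the first subject is randomised. The primary interval and the ANCOVA terms are methods that the protocol itself fixes.

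**Working it through.** **Inputs from the protocol.** 135 evaluable per arm (150 randomised, 10% dropout); planning rates 85% v 75% (CD4+) and 55% v 45% (CD8+); margin 10 points; one-sided 0.025 (8.2, 8.4.2).

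**Assumed inputs.** The share over 70 and the size of any age effect are not in the protocol. They are varied below.

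**1. The plan's own power.** Power = Φ[(difference + 0.10)/SE − 1.96], with SE = √{[p₁(1−p₁) + p₂(1−p₂)]/n}.
- CD4+: SE = √[(0.1275 + 0.1875)/135] = 0.0483; Φ(0.20/0.0483 − 1.96) = Φ(2.18) = 98.5%.
- CD8+: SE = √[(0.2475 + 0.2475)/135] = 0.0606; Φ(0.20/0.0606 − 1.96) = Φ(1.34) = 91.0%.
- Both together, if independent: 0.985 × 0.910 = 89.7%.

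This agrees with the roughly 90% stated in 8.2. A simulation of the Miettinen-Nurminen test gave 98.6% and 91.1%.

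**2. Chance imbalance.** With share s over 70 and an age effect d on response, the imbalance shifts the difference with SD = d × √[2s(1−s)/150]. For s = 0.25 and d = 0.20: 0.20 × √(2 × 0.1875/150) = 0.010. That is 1 point, or about ±2 points as a 95% range.

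**3. Precision given up (CD8+).** If the age effect d is common to both arms, stratifying lowers the variance by about s(1−s)d²/0.2475.

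| Share over 70 | Age effect | Variance reduction | CD8+ power |
|---|---|---|---|
| 15% | 20 points | 2.1% | 91.6% |
| 25% | 20 points | 3.0% | 91.8% |
| 15% | 30 points | 4.6% | 92.3% |
| 25% | 30 points | 6.8% | 92.8% |

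The last row, for example: SE = 0.0606 × √(1 − 0.068) = 0.0585, and Φ(0.20/0.0585 − 1.96) = Φ(1.46) = 92.8%.

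**4. Would stratifying expose a deficit above 70?** Suppose LZ901 is 10 points better up to age 70 and 20 points worse above it, with control flat across ages. With 20 of 135 per arm over 70, the pooled difference is (115 × 10 − 20 × 20)/135 = +5.6 points. Simulated pass rates, using Wald intervals with and without age strata and the age split held fixed:

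| Over 70 per arm | Endpoint | Unstratified | Stratified |
|---|---|---|---|
| 20 | CD8+ | 73% | 73% |
| 20 | CD4+ | 87% | 88% |
| 34 | CD8+ | 54% | 55% |
| 34 | CD4+ | 68% | 70% |

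Both analyses average over the age bands, so stratifying does not reveal the deficit.

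**5. Precision within the over-70 band.** At 20 per arm, the CD8+ 95% half-width is 1.96 × √(2 × 0.55 × 0.45/20) = 0.31, or 31 points.

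**The case against.** The strongest defence is that nothing here is invalid. Unstratified 1:1 randomisation gives an unbiased comparison, and chance imbalance is already covered by the confidence interval: an SD of 1 point is small beside the CD8+ standard error of about 6 points. The stated power reproduces. Enrolling the comparator's approved age range is coherent, and it is how data above 70 are obtained. All of this stands, and it keeps the point small.

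A reader might infer more: that a poor T-cell response above 70 could pass without anyone noticing. The documents do not support that. The pooled test can pass despite such a deficit under step 4's assumptions, but those assume that LZ901 alone declines with age. The protocol's remark on age is general, and 3.2.1 reports lower zoster efficacy for the control vaccine at 70 and over (89.8%) than at 50 and over (97.2%), so a flat control is not a natural assumption. An equal decline in both arms leaves the difference unchanged. An age-band table is ordinary SAP content, and the SAP is not at hand. The ANCOVA concerns antibodies, so adding age there says nothing about T cells.

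Three further inferences fail. It cannot be said that LZ901 has been tested only at 50-70, because 1.2.3 and 3.2.3.2 mention a Phase III trial without giving ages. Nothing ranks age as the main determinant of the endpoint; 1.1 lists it among several causes of impaired immunity. And the synopsis's wish for a relatively balanced sex mix is no argument for stratifying, since strata balance sex between arms and do not set the overall ratio.

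**Conclusion.** The point holds as a low-cost improvement, not as an error. The protocol extends enrolment beyond the ages of its reported LZ901 Phase I/II data, gives a reason why age may matter, and then fixes an allocation scheme, a primary interval and an ANCOVA that ignore it.

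The cost is an SD of about 1 point from chance imbalance (25% over 70, 20-point age effect), and a CD8+ variance about 2-7% larger than it need be, or power of about 91% where 91-93% was available (15-25% over 70, 20-30 point age effect common to both arms). These figures rest on an age mix and age effects that the protocol does not give; with fewer subjects over 70 or a weaker age effect, the gain shrinks towards nothing.

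Separately, the pooled result alone would say little about people over 70. Stratifying does not change that.

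**What to change.** - **Section 5.5.2:** stratify the central block randomisation by age (50-70, over 70). If allocation is already complete, leave it and stratify the analysis only.
- **Section 8.4.2:** make the Miettinen-Nurminen difference stratified by the same age band the primary CD4+ and CD8+ comparison, with the margin and decision rule unchanged.
- **Section 8.4.3:** add age to the antibody ANCOVA.
- **Recommendation, unless the SAP already has it:** show the CD4+ and CD8+ differences with 95% intervals in each age band, and word the conclusion for the ages actually enrolled.

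The cost is one factor in a randomisation system already in use, one option in the analysis code and at most one extra table. No further subjects or data are needed. The over-70 intervals will be wide and should be presented as descriptive.

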5.5.3 Blinding and Unblinding

5.5.3.1 Blinding

This study adopts a partially blinded design. Vaccine blinding is conducted by the randomization statistician along with other blinding personnel. Pre-printed vaccine labels are affixed to each designated vaccine position according to the randomization code. The randomization statistician oversees the blinding process, guiding blinding personnel to label the vaccines according to the randomization code. Once blinding is complete, the randomization code should be sealed by the randomization statistician. The entire blinding process must be documented in writing. Blinding personnel are prohibited from participating in any other activities related to this study and must not

disclose the randomization code to any study personnel. Preparation and administration of the experimental/control vaccine will be handled by authorized medical staff who are not involved in the clinical evaluation of subjects.

5.5.3.2 Unblinding Procedures

In this study, unblinding is required before the administration of the second dose, as the dosing intervals differ between the experimental group (30 days) and the control group (60 days). The unblinding process must be initiated by the principal investigator, who submits an unblinding request to the sponsor, and a record of the unblinding must be maintained.

In the event of group adverse events or study interruption for any reason, early unblinding may be conducted with the mutual agreement of the sponsor and the research team.

5.5.3.3 Emergency Unblinding

During the study, individual emergency unblinding may only be conducted if a serious adverse event (SAE) occurs, the subject requires emergency rescue or treatment, and the product information is critical for the subject clinical management. In such cases, a researcher with unblinding authority at the study site should access the Clinflash IRT system to document the reason for unblinding and initiate emergency unblinding. The researcher must report the unblinding within 24 hours to the principal investigator or lead sub-investigator, promptly notify the sponsor and the sponsor designated CRO, and provide a written explanation to the sponsor.

The study will be terminated for the subject with the specific study number (while safety follow-up will continue), and the reason for termination should be documented in the case report form.

The investigator or any other physician managing the subject should contact the sponsor to discuss the necessity of emergency unblinding.

An emergency unblinding request should only be made if there is a medical emergency or serious condition where the study vaccine information is crucial to the subject clinical care or welfare.

The sponsor will permit unblinding only if the investigator responsible for the subject believes that the medical event cannot be managed without knowing the identity of the study vaccine.

5.6 Study Intervention Compliance

To ensure and document vaccination information and compliance with study interventions, subjects are required to remain on-site for 30 minutes after each dose of the study vaccine. The researcher provides each subject with a Diary Card, thermometer, and ruler, instructing them to measure and record their body temperature (axillary temperature) and note any adverse events for 7 days following vaccination. Subjects are trained on how to use the thermometer and ruler, how to observe adverse events, and

how to complete the Diary Card. The Diary Card is collected on day 7 post-vaccination, at which time subjects are also given a Contact Card for recording all adverse events occurring from day 7 to day 30 post-vaccination. The Contact Card is collected and reviewed 30 days after each dose.

6. Discontinuation of Study Intervention and Subject Withdrawal from the Study

6.1 Discontinuation of Study Intervention

6.1.1 Postponement Criteria for the Second Vaccination

The study intervention (second dose of vaccine) should be temporarily suspended (or delayed) until the situation resolves in the following cases:

- 1) Axillary temperature > 37.0°C/99.0°F;
- 2) Acute illness within 3 days prior to vaccination (e.g., acute upper respiratory infection with symptoms such as fever, cough, sore throat, difficulty breathing) or during an acute stage of a chronic disease, or use of antipyretics, analgesics, or antihistamines;
- 3) Insufficient interval between vaccinations (receiving an inactivated vaccine, recombinant vaccine, or mRNA vaccine within 14 days prior to vaccination, or any live attenuated vaccine within 28 days prior to vaccination);
- 4) Any Grade 3 or higher adverse event on the day of vaccination;
- 5) Other circumstances where the investigator considers vaccination should be delayed.

6.1.2 Exclusion Criteria for the Second Dose

The investigator will terminate the administration of the second dose of the study vaccine if any of the following occur:

- 1) Any serious adverse event (SAE) related to the vaccination;
- 2) Severe allergic reaction following vaccination;
- 3) Suspected varicella-zoster virus (VZV) infection after the first dose of vaccination;
- 4) Discovery of any new condition that meets the "exclusion criteria for the first dose";
- 5) Any other reason, as determined by the investigator, that requires discontinuation of the study vaccine administration.

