4.4 Exclusion criteria

- 1) History of herpes zoster within the past 5 years.
- 2) Previous vaccination with varicella vaccine or zoster vaccine (including use of registered products or participation in clinical trials for varicella or zoster vaccines).
- 3) Allergy to any component of the study vaccine: Previous allergy to any recombinant vaccine derived from CHO cells (such as recombinant hepatitis B vaccine [CHO cells]), polysorbates, or a history of severe allergic reactions* to any

vaccination.

- a) *Severe allergic reactions: Anaphylactic shock, allergic laryngeal edema, allergic purpura, thrombocytopenic purpura, localized allergic necrotic reaction (Arthus reaction), severe urticaria, etc.
- 4) Diagnosis of immune deficiency diseases (such as congenital or acquired immunodeficiency, HIV infection, etc.), or receiving immunosuppressive/cytotoxic treatment (e.g., chemotherapy, organ transplantation, or planned treatment during the clinical trial within 6 months before vaccination).
- 5) Subjects who received immunosuppressive therapy within 3 months before vaccination, or planning to receive such treatment within 1 month after full immunization (e.g., long-term use of systemic glucocorticoids for \geq 14 days, dose \geq 2 mg/kg/day or \geq 20 mg/day prednisone or equivalence);
- 6) Receiving an inactivated vaccine, recombinant vaccine, or mRNA vaccine within 14 days or any live vaccine within 28 days prior to vaccination;
- 7) Subjects with acute illness or in the acute phase of a chronic disease within 3 days prior to vaccination.
- 8) Asplenia or splenectomy.
- 9) Subjects who receive blood products or immunoglobulin therapy within 3 months before vaccination, or planning to use such products within 2 months after vaccination.
- 10) Participating in other clinical studies of investigational or un-registered products (drugs, vaccines or devices, etc.), or planning to participate in other clinical studies before the end of this clinical study.
- 11) Any significant underlying medical condition (e.g., life-threatening diseases that may limit survival to less than 4 years) or other conditions that the investigator believes may interfere with the completion of the study.

Exclusion Criteria for the Second Dose

The investigator will terminate the administration of the second dose of the study vaccine if any of the following occur:

- 1) Any serious adverse event (SAE) related to the vaccination;
- 2) Severe allergic reaction following vaccination;

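### Acute illness or a recent other vaccine both delays and terminates dose 2, with no rule of precedence; separately, the 37.0°C/99.0°F limit states two different temperatures

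*Protocol*

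**What the plan says.** **Postponement (Protocol 6.1.1, repeated in the synopsis).** Dose 2 "should be temporarily suspended (or delayed) until the situation resolves in the following cases". Item 1 is "Axillary temperature > 37.0°C/99.0°F". Item 2 begins "Acute illness within 3 days prior to vaccination" and also covers the acute stage of a chronic disease. Item 3 is "Insufficient interval between vaccinations", which it explains as "receiving an inactivated vaccine, recombinant vaccine, or mRNA vaccine within 14 days prior to vaccination", or a live attenuated vaccine within 28 days.

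**Termination (Protocol 6.1.2, repeated in the synopsis and at the end of 4.4).** The investigator is to terminate dose 2 in five situations. Item 4 is "Discovery of any new condition that meets the" exclusion criteria for the first dose. It imports the whole list and exempts no temporary condition.

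**First-dose exclusions (Protocol 4.4).** Item 6 is "Receiving an inactivated vaccine, recombinant vaccine, or mRNA vaccine within 14 days or any live vaccine within 28 days prior to vaccination". Item 7 is "Subjects with acute illness or in the acute phase of a chronic disease within 3 days prior to vaccination".

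**Analysis sets (Protocol 8.3).** The FAS and the PPS both require completed vaccination. The PPS also drops subjects with major deviations that affect immunogenicity. Section 8.4.2 makes the PPS the main set for the primary endpoint.

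**The concern.** One event at the dose-2 visit has two prescribed outcomes, one temporary and one final. Two sites that each follow the text could treat the same subject differently. Because both immunogenicity sets require completed vaccination, that choice helps to decide who is in the primary analysis.

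It is also made with the arm known: Section 5.5.3.2 requires unblinding before dose 2, and the synopsis calls the study open-label at that point. An unresolved stop-or-delay rule therefore leaves room for discretion where blinding no longer protects.

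The temperature limit is a separate and smaller fault. It is written in two units that do not agree, and it governs both enrolment (inclusion criterion 4) and the timing of dose 2.

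**Working it through.** **1. The two rules side by side**

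| Event before dose 2 | Under 6.1.1 | Under 6.1.2 item 4 |
|---|---|---|
| Acute illness, or acute phase of a chronic disease, within 3 days | item 2: delay | exclusion 7: terminate |
| Inactivated, recombinant or mRNA vaccine within 14 days | item 3: delay | exclusion 6: terminate |
| Live vaccine within 28 days | item 3: delay | exclusion 6: terminate |

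The conditions and look-back periods match. The rest of 6.1.1 is outside the conflict: temperature is an inclusion criterion, and use of antipyretics, analgesics or antihistamines and a Grade 3 event on the day are not on the 4.4 list.

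**2. Does other text settle it?**

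- The Schedule of Activities re-checks inclusion and exclusion criteria at the dose-2 visit (D30 experimental, D60 control), so exclusions 6 and 7 are applied again there.
- Section 5.1.7 allows dose 2 to be postponed or interrupted but points only to 6.1.1.
- Section 4.5 lets a subject who temporarily fails a criterion be re-screened, but only before enrolment.
- Section 5.1.10.2 leaves emergency vaccination unrestricted. A subject who has one shortly before dose 2 meets both rules.

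None of these ranks the two sections.

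**3. Effect on the analysis sets**

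A terminated subject has not completed vaccination and is in neither set. A delayed subject who later receives dose 2 can be in the FAS. For the PPS, the window in Section 5.1.7 (−2/+7 days) matters. The last in-window day is 30 + 7 = 37 in the experimental arm and 60 + 7 = 67 in the control arm. If another vaccine is given on day t, dose 2 can follow from t + 14 (non-live) or t + 28 (live), so it stays in the window only when:

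- non-live: t ≤ 37 − 14 = 23 (experimental), or t ≤ 67 − 14 = 53 (control);
- live: t ≤ 37 − 28 = 9 (experimental), or t ≤ 67 − 28 = 39 (control).

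Section 5.1.10.2 puts other non-emergency vaccines at least 14 days after a study dose. In the experimental arm, a live vaccine given in line with that rule moves dose 2 to day 14 + 28 = 42 at the earliest, 5 days past the window. Whether a late dose 2 is a major deviation is not stated. Section 8.5 does not name the window, though Section 7.6 asks evaluable subjects to have kept to the protocol intervals.

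**4. Temperature**

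- 37.0 × 9/5 + 32 = 98.6°F, not 99.0°F.
- (99.0 − 32) × 5/9 = 37.22°C, not 37.0°C.
- Gap: 0.4°F, or 0.22°C.
- 37.1°C = 98.78°F and 37.2°C = 98.96°F. Both exceed 37.0°C and both are below 99.0°F.

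The same pair stands in the synopsis (inclusion and postponement), in 4.3 item 4 and in 6.1.1 item 1.

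**The case against.** The strongest reply is that the specific rule qualifies the general one. Section 6.1.1 names these conditions and foresees their resolution, whereas 6.1.2 item 4 is a catch-all. Other text leans the same way: Section 5.1.10.2 permits some vaccination between doses, and Section 7.5.1 calls pregnancy an exclusion for each dose yet only defers dose 2. Counting a vaccination as a new condition also takes a reading step, so the overlap is clearest for acute illness. This makes divergent conduct less likely, but it remains inference: the termination wording is mandatory and no precedence is stated.

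On temperature, the Fahrenheit figure may be a rounded courtesy value. The fever grading in Section 11.3 uses Celsius only, and the gap is small. That supports calling it minor. It does not make the two figures agree.

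Two stronger readings are tempting, and the document does not support them.

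- **That exposure to the conflict differs by arm because controls wait 60 days and not 30.** The triggers are fixed look-backs of 3, 14 and 28 days ending at the dose, so an illness on day 20 that has resolved triggers neither rule at day 30 or day 60. At most, non-emergency live vaccines differ: given the 14-day spacing rule, the usable part of the 28-day look-back is days 14–30 (16 days) in the experimental arm and days 32–60 (28 days) in the control arm.
- **That a quantifiable amount of power is lost.** No stop rate is given, and the 135 evaluable subjects per group in Section 8.2 already allow 10% dropout from 150, which can include subjects who miss dose 2.

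**Conclusion.** The point holds as an inconsistency in the protocol's wording. For acute illness and for a recent other vaccine, 6.1.1 and 6.1.2 item 4 prescribe different consequences, no text ranks them, and the choice falls after unblinding. Applied literally, item 4 removes from dose 2, and so from the FAS and the PPS, subjects whom 6.1.1 would keep in the dosing schedule.

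The contrast between stopped and delayed subjects is clean only for the FAS. A delayed subject keeps a place in the PPS only if the delay is not judged a major deviation from the −2/+7 day window.

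The conclusion rests on reading termination as final, against a delay that ends on resolution. For the vaccine trigger it also rests on treating a vaccination as a new condition because it is first-dose exclusion 6. The number of subjects affected is unknown, and no sample-size input is shown to be wrong.

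The temperature mismatch is certain but small, at 0.22°C. It matters for subjects at 37.1 or 37.2°C. At enrolment, failing an inclusion criterion is a listed violation in Section 8.5, and the PPS requires the criteria to be met. The protocol does not say how many subjects fall in that gap.

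**What to change.** - Reconcile 6.1.1 items 2 and 3 with 6.1.2 item 4, and the matching text in the synopsis and in 4.4, so that each event has exactly one stated consequence.
- State one axillary limit with agreeing Celsius and Fahrenheit values in inclusion criterion 4, in 6.1.1 item 1 and in the synopsis.

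Which consequence and which temperature apply is for the sponsor's clinical team to decide. The cost is a wording amendment and a memo to sites. Design, endpoints and sample size do not change.
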